10.3 Planned Analyses

10.3.1 Interim Analyses

Amgen will conduct evaluations of the ongoing DLT rate to assess if the threshold for early trial termination as defined in [Section 6.2.2](#) has been reached. The stopping rules use a Bayesian approach to terminate the study if the posterior probability that the DLT rate is greater than 25% is > 90%. The stopping boundaries assume a prior distribution of (0.50, 1.50) are presented in [Table 7](#) and the operating characteristics with pre-specified batch size of 10 new subjects per batch are presented in [Table 8](#). The

evaluations could occur more frequently if necessary to address emerging safety concerns. The operating characteristics in [Table 8](#) provide the probability of stopping the trial early for given hypothetical true DLT rates, whereas the stopping criteria in [Table 7](#) are based on situations where the empirical evidence would result in a posterior probability of $\geq 90\%$ that the true DLT rate is $\geq 25\%$.

Table 7. Stopping Boundary With Posterior Probability of 90% and DLT Limit of 25%

Number of DLT evaluable subjects (inclusive)	Stop study if observing these many DLTs
10	≥ 5
20	≥ 8
30	Study completes

DLT = dose limiting toxicity

Table 8. Operating Characteristics With Batch Size of 10 Subjects

True DLT rate	Probability of stopping	Average sample size
0.20	5%	30
0.25	14%	28
0.30	27%	26
0.35	44%	24
0.40	62%	21

DLT = dose limiting toxicity

10.3.2 Data Review Team

A DRT will review safety data periodically. A DRT is a group, internal to Amgen but external to the relevant blinatumomab product team, that reviews accumulating data from the ongoing clinical trial to ensure no avoidable increased risk for harm to subjects. Continuous toxicity monitoring for early termination of the trial will be performed. Adverse events and DLTs (as defined in [Section 6.2.2](#)) observed in all subjects will be evaluated every 10th subject or every 6 months, whichever occurs earlier. The DRT includes a clinician, a safety physician, and a biostatistician. Membership, procedures, and meeting timing will be described in detail in the study DRT charter.

10.3.3 Primary Analysis

The objective of the primary analysis is to estimate the primary endpoint, MRD-negative rate at the end of cycle 1 of blinatumomab. All subjects in the treatment period are considered MRD positive, regardless whether the cycle 1 day 1 MRD test results are

positive or negative because these subjects have been tested MRD positive in the run-in period. The primary analysis will be triggered when the first 30 enrolled subjects have had the opportunity to complete cycle 1 of blinatumomab treatment. Any subjects treated beyond the required sample size of 30 subjects will not be part of the primary analysis. The safety and tolerability of blinatumomab will also be assessed at the time of the primary analysis.

At the time of the primary analysis the following will be obtained using the pre-treatment analysis set: estimates of the rate and timing of conversion from MRD-negative to MRD positive, and exploratory endpoints of MRD status by the NGS MRD test in PET-CT negative subjects.

10.3.4 Final Analysis

The main objective of the final analysis is to provide estimates of the secondary and exploratory endpoints. The final analysis will also include updated estimates for the endpoints assessed at the primary analysis (MRD-negative rate and MRD prior to blinatumomab treatment). The updated estimates will include all subjects enrolled in the study who received at least one dose of blinatumomab. This would include any subjects treated after the expected sample size of 30 subjects.

A sensitivity analysis will be performed on the time to event endpoints in relation to MRD-negative versus no MRD-negative.

The other exploratory endpoints will also be assessed at the point of the final analysis.

The final analysis will be conducted when the subjects in the Primary Analysis Set have had an opportunity to complete the long-term follow-up visit 1 year from the first dose of blinatumomab.

The final analysis will also assess the potential long-term effect of blinatumomab on safety.

10.4 Planned Methods of Analysis

10.4.1 General Considerations

Continuous variables will be summarized by the non-missing sample size (n), mean, standard deviation, median, first and third quartiles, minimum, and maximum.

Categorical variables will be summarized by the n and percentage in each category.

Time to event endpoints will be summarized with Kaplan-Meier (KM) curves, KM proportions at selected time points, KM quartiles (when estimable), the number of subjects with events, the number of subjects censored, and the pattern of censoring.

Point estimates for efficacy endpoints will be accompanied by 2-sided 95% CI including estimates of KM quartiles ([Brookmeyer and Crowley, 1982](#)), KM proportions ([Kalbfleisch and Prentice, 1980](#)), and binomial proportions ([Clopper and Pearson, 1934](#)).

No adjustments for multiplicity are planned for the analyses of the efficacy endpoints.

10.4.2 Primary Efficacy Endpoint

MRD-negative rate at the end of cycle 1 of blinatumomab. MRD is defined as negative when the tumor clone sequence in plasma is below the assay's limit of detection (to be determined in the assay validation).

MRD-negative rate is calculated as the number of subjects with MRD-negative status after treatment with blinatumomab divided by the total number of subjects in the respective analysis set.

Exact binomial 95% CI will be used to analyze MRD-negative rate.

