6.2.1.3 Permanent Discontinuation of Blinatumomab

Blinatumomab will be permanently discontinued for:

Disease Progression

Cytokine Release Syndrome

- Initial grade 3 CRS that does not improve to grade ≤ 1 within 7 days
- Grade 3 CRS that reoccurs at the lower dose level within 7 days of reinitiation
- Grade 3 CRS reoccurs at a dose of 9 $\mu\text{g}/\text{day}$ without prior dose-step escalation
- Grade 4 CRS

Neurologic Events

- Initial grade 3 neurologic event occurred at 9 $\mu\text{g}/\text{day}$
- Initial grade 3 neurologic event does not improve to grade ≤ 1 within 7 days
- Grade 3 neurologic event that reoccurs at the lower dose level within 7 days of reinitiation
- Grade 3 neurologic event reoccurs at a dose of 9 $\mu\text{g}/\text{day}$
- Grade 4 neurologic event
- A second seizure occurs after reinitiation of blinatumomab at any dose

Elevated Liver Enzymes

- Total bilirubin (TBL) $> 2 \times$ ULN OR international normalized ratio (INR) > 1.5 (for subjects not on anticoagulant therapy) AND
- AST/ALT $> 3 \times$ ULN (when baseline was $< \text{ULN}$) AND
- No other cause of combination of the above laboratory abnormalities is immediately apparent

Other Clinical Relevant Adverse Events

- Initial grade 3 event does not improve to grade ≤ 1 within 14 days (with the exception of delay in restart due to logistical difficulties, in which case the restart may be postponed for an additional 7 days)
- Grade 3 event reoccurs at the lower dose level within 7 days of reinitiation
- Grade 3 event reoccurs at a dose of 9 $\mu\text{g}/\text{day}$ without prior dose-step escalation
- Dose limiting toxicities (DLTs) as described in [Section 6.2.2](#)

Subjects who permanently discontinue study treatment due to adverse event should continue with other study procedures, including response assessment, as appropriate.

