6.8 Excluded Treatments, Medical Devices, and/or Procedures During Study Period

The following treatments and/or procedures are excluded during the study:

- Any antitumor therapy other than blinatumomab
- Any other immunosuppressive therapies (except for transient use of corticosteroids)
- Any other investigational agent
- Cytotoxic and/or cytostatic drugs
- Radiation therapy
- Immunotherapy other than blinatumomab
- Chronic systemic (> 7 days) high-dose corticosteroid therapy (dexamethasone > 24 mg/day or equivalent)

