8.3.2 Reasons for Removal From Treatment

Reasons for removal from protocol-required investigational product(s) or procedural assessments include any of the following:

- subject request
- safety concern (eg, due to an adverse event, ineligibility determined, protocol deviation, non-compliance, requirement for alternative therapy, pregnancy)
- death
- lost to follow-up
- decision by sponsor (other than subject request, safety concern, lost to follow-up)
- disease progression
- other protocol-specified criteria as described in [Section 6.2.1.3](#)

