10.4.3 Secondary Efficacy Endpoint(s)

PFS is calculated as the time from the date of first dose of blinatumomab until the date of diagnosis of relapse of lymphoma (by PET-CT, CT, clinical assessment or relapse biopsy, whichever is the preferred method), or date of death, whichever is the earliest. Subjects alive who did not have progression or new anti-tumor treatment (excluding any stem cell transplantation) will be censored at last date of tumor assessment.

The duration of MRD-negative status will be assessed only in subjects who achieve MRD-negative status after blinatumomab treatment. Duration of MRD-negative status will be defined from the time when a negative MRD result is first established until documented MRD-positive reoccurrence, or disease progression (or, death due to any cause). Subjects without any of these events at the time of the analysis will be censored at their last disease assessment date.

Overall survival will be defined from the first dose of blinatumomab treatment until death due to any cause. Subjects still alive at the time of the analysis will be censored at date last known to be alive.

PFS, duration of MRD-negative status and OS will be summarised with KM analyses.

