6.2 Primary Analysis Set

The primary analysis set will include the first 30 enrolled subjects who received at least 1 dose of blinatumomab. The primary analysis set will be used for the primary analysis.

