9.5 Efficacy Analyses

Table 9-1. Primary Efficacy Endpoint Summary Table

Endpoint	Primary Summary and Analysis Method	Sensitivity Analysis
Proportion of subjects who achieve MRD response (MRD negativity) after cycle 1 of blinatumomab. MRD negativity is determined as the best MRD response on day 57 or day 71(+3 days) via MRD testing.	The MRD-negative rate at the end of cycle 1 of blinatumomab is calculated as the number of subjects with MRD-negative status after treatment with blinatumomab divided by the total number of subjects in the Primary Analysis Set for Primary Analysis. Exact binomial 95% CI will be summarized. The Full Analysis Set will be used at final analysis..	A sensitivity analysis will be performed using the Target Dose Analysis Set for the final analysis.

Table 9-2. Secondary Efficacy Endpoint Summary Table

Endpoint	Primary Summary and Analysis Method	Sensitivity Analysis
PFS	Kaplan-Meier (KM) analyses (KM plot and KM estimates) on the Full Analysis Set.	A sensitivity analysis will be performed using the Target Dose Analysis Set for the final analysis
Duration of MRD-negative status	Kaplan-Meier (KM) analyses (KM plot and KM estimates) on the Full Analysis Set.	A sensitivity analysis will be performed using the Target Dose Analysis Set for the final analysis
OS	Kaplan-Meier (KM) analyses (KM plot and KM estimates) on the Full Analysis Set.	A sensitivity analysis will be performed using the Target Dose Analysis Set for the final analysis.

Secondary efficacy endpoints will be assessed only at final analysis.

Table 9-3. Exploratory Efficacy Endpoint Summary Table

Endpoint	Primary Summary and Analysis Method	Sensitivity Analysis
MRD-negative rate	The MRD-negative rate will be summarized at each time point measured following blinatumomab treatment using both Primary and Full Analysis Sets.	A sensitivity analysis will be performed using the Target Dose Analysis Set for the final analysis
Incidence of alloHsCT	Incidence of alloHsCT (number of subjects with alloHsCT), including the methodology (Intensity of Conditioning Regimen and Donor Type) and clinical outcomes (Maximum grade of aGVHD) will be summarized using Full Analysis Set.	A sensitivity analysis will be performed using the Target Dose Analysis Set for the final analysis

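### A negative MRD sample taken after another anti-lymphoma therapy has begun would count as a blinatumomab response, because the primary endpoint has no rule for such samples

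*Protocol*

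**What the plan says.** The numerator in Protocol 10.4.2 depends only on the MRD result: "MRD-negative rate is calculated as the number of subjects with MRD-negative status after treatment with blinatumomab". SAP Table 9-1 fixes the timing: "MRD negativity is determined as the best MRD response on day 57 or day 71(+3 days) via MRD testing". One negative sample of the two is therefore enough. Early stoppers stay in the denominator, since SAP 6.2 reads: "The primary analysis set will include the first 30 enrolled subjects who received at least 1 dose of blinatumomab".

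Subjects who stop early are meant to stay under observation. Protocol 6.2.1.3 says: "Subjects who permanently discontinue study treatment due to adverse event should continue with other study procedures, including response assessment, as appropriate". Protocol 8.1 also presses for outcome data to be collected after treatment stops.

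Three provisions come near the issue without settling it:
- Protocol 6.8 excludes "Any antitumor therapy other than blinatumomab" during the study, but does not say how a subject who receives it is analysed.
- Protocol 10.1.4 treats missing post-baseline MRD as not MRD-negative. It is the only rule that makes a subject a non-responder for a reason other than the test result.
- Protocol 10.4.3 mentions new anti-tumor treatment in its PFS censoring sentence, leaving stem cell transplantation out of that term. The SAP Section 5 PFS definition omits the mention, although SAP Section 10 reports no changes from the protocol. The primary endpoint has no counterpart in either document.

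The secondary endpoint inherits the gap. Protocol 10.4.3 says: "Duration of MRD-negative status will be defined from the time when a negative MRD result is first established until documented MRD-positive reoccurrence". Nothing there addresses other therapy.

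**The concern.** The primary objective is MRD negativity following blinatumomab, and no control arm would reveal clearance caused by another drug. Any misattribution raises the reported rate.

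Two routes are open under the written rule. First, a subject stops early for toxicity or at their own request, starts another therapy, and is negative on day 57 or day 71. Permanent discontinuation can fall in week 1, for example after a grade 3 neurologic event at the starting dose (Protocol 6.2.1.3). Second, a subject is positive on day 57, starts another therapy, and is negative on day 71; the best-of-two rule counts that subject.

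The result would also depend on site conduct. The same subject is a failure under Protocol 10.1.4 if the site takes no sample, and a success if it samples and the result is negative.

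**Working it through.** **Inputs.** N = 30, reference rate 10% and rate of interest 30% (Protocol 10.2, SAP 2.2 and 3.2). Two-sided exact 95% Clopper-Pearson limits (Protocol 10.4.1). The documents give no number of subjects who would start another therapy and no clearance rate on it, so both are assumptions below.

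**Reproducing the plan's figures.** With x responders of n, the lower limit is the 0.025 quantile of Beta(x, n − x + 1) and the upper limit the 0.975 quantile of Beta(x + 1, n − x). For x = 8, 9, 11, 12 and 14 of 30 this gives 12.3–45.9, 14.7–49.4, 19.9–56.1, 22.7–59.4 and 28.3–65.7. All five rows of SAP Table 3-1 agree.

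**Where the 10% reference is crossed.**

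| Responders | Rate | Exact 95% CI | Lower limit above 10%? |
|---|---|---|---|
| 7/30 | 23.3% | 9.9 to 42.3 | No (9.93) |
| 8/30 | 26.7% | 12.3 to 45.9 | Yes (12.28) |

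One subject is worth 1/30 = 3.3 points, and one is enough to cross. The implied criterion is at least 8 of 30.

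**Chance of reaching 8/30 at a true rate of 10%.** If exactly k subjects are negative because of another therapy and the other 30 − k respond at 10%, the chance is P[Bin(30 − k, 0.10) ≥ 8 − k].

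- k = 0: P[Bin(30, 0.10) ≥ 8] = 0.0078, or 0.8%
- k = 1: P[Bin(29, 0.10) ≥ 7] = 0.0216, or 2.2%
- k = 2: P[Bin(28, 0.10) ≥ 6] = 0.0550, or 5.5%

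**Wider range.** Suppose 1 to 4 of the 30 start another therapy and are sampled, each turning negative with probability 25% to 75%, and the rest respond at 10%. The expected observed rate then runs from 10.5% to 18.7%, and the chance of at least 8/30 from 1.0% to 13.8%. With those subjects counted as not MRD-negative, the expected rate is 9.7% (one subject) down to 8.7% (four), and the chance 0.6% down to 0.3%.

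**Does the Target Dose set close the gap?** It requires at least 7 days at the highest intended dose, or a stop for progression in cycle 1 (Protocol 10.1.2.3, SAP 6.3). The 112 µg/day step starts on day 15, so on the planned schedule 7 days are complete after day 21. Earlier stops for toxicity or by request drop out. Later stops, and progression stops at any time, stay in. SAP 9.5.1 uses this set only at the final analysis, so the primary analysis has no such check.

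**The case against.** The strongest reply is that the route is narrow, and much of that stands.

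- Treated subjects must be PET-CT negative (criterion 113), and Protocol 2.6 describes options after transplant as very limited. A toxicity stop in remission gives no evident reason for new lymphoma therapy within weeks. Protocol 6.8 prohibits it in any case.
- Day 57 and day 71 samples may not be taken. A subject stopped on day 8 has a safety visit around day 38 (8 + 30) and then visits every 3 months, so sampling rests on the response-assessment sentence in 6.2.1.3 and its closing qualifier. After relapse in long-term follow-up, contact is by telephone. Unsampled subjects count as failures.
- The phrase "requirement for alternative therapy" in Protocol 8.3.2 is one example within a list of safety concerns, "non-compliance, requirement for alternative therapy, pregnancy". A reader might infer that it foresees lymphoma rescue specifically; the text does not say so.
- The SAP plans no formal hypothesis test, so the probabilities above describe how often the interval would exclude 10%, not a formal type I error.

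These points limit how many subjects are affected. They do not change how such a subject is counted: a protocol deviation neither removes a subject from the Primary Analysis Set nor alters the MRD result.

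**Conclusion.** The gap is real and worth closing before the primary analysis. Under the written rule, a negative sample taken after another anti-lymphoma therapy enters the numerator. This follows from silence. A reader might infer that the plan expressly instructs such subjects to be counted as responders; no section says that.

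The direction is certain, but the size is not. One subject can move the interval across 10%, and one or two certain extra responders raise the chance of at least 8/30 at a true 10% from 0.8% to 2.2% or 5.5%. Those counts are assumptions, and the true number is probably small.

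Two stronger readings are not supported:
- Raising the response rate of all 30 subjects to 13.3% or 16.7% gives 3.9% and 11.4%. Those figures are too high for the scenario of exactly one or two affected subjects.
- The 25% DLT figure might suggest 7 to 8 early stops (0.25 × 30 = 7.5), and from there one or two cleared by other therapy. But 25% is a safety limit rather than an expected rate, DLTs can occur anywhere in cycle 1, and nothing in the documents links stops to new therapy.

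**What to change.** In Protocol 10.4.2 and in SAP Section 5, 9.5.1 and Table 9-1, state the following:

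1. MRD samples collected after the start of non-protocol anti-lymphoma therapy do not count towards MRD-negative status.
2. A subject with no qualifying negative day 57 or day 71 sample before that therapy stays in the denominator as not MRD-negative. A subject with a qualifying negative sample before it remains a responder, so someone negative on day 57 who starts therapy on day 60 is not reclassified.
3. The count regardless of other therapy is kept as a sensitivity analysis, and the number of affected subjects is reported.
4. AlloHSCT is handled in a separate sensitivity analysis. The protocol studies alloHSCT as an outcome and leaves stem cell transplantation out of new anti-tumor treatment for PFS, so counting it as failure in the main analysis would contradict its own approach.
5. Duration of MRD-negative status gains a sensitivity analysis censored at the last assessment before new anti-lymphoma therapy.

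The cost is SAP wording and one derived flag. Protocol 6.5 collects concomitant therapy with start dates through safety follow-up, and the Schedule of Assessments has an anti-lymphoma therapy row for long-term follow-up; confirm that the latter captures start dates. No visit, sample or clinical rule changes. The reported rate can only stay the same or fall slightly. A subject cleared by day 43 who starts other therapy before day 57 would count as not MRD-negative, and the sensitivity count in item 3 would show that.

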10.4.3 Secondary Efficacy Endpoint(s)

PFS is calculated as the time from the date of first dose of blinatumomab until the date of diagnosis of relapse of lymphoma (by PET-CT, CT, clinical assessment or relapse biopsy, whichever is the preferred method), or date of death, whichever is the earliest. Subjects alive who did not have progression or new anti-tumor treatment (excluding any stem cell transplantation) will be censored at last date of tumor assessment.

The duration of MRD-negative status will be assessed only in subjects who achieve MRD-negative status after blinatumomab treatment. Duration of MRD-negative status will be defined from the time when a negative MRD result is first established until documented MRD-positive reoccurrence, or disease progression (or, death due to any cause). Subjects without any of these events at the time of the analysis will be censored at their last disease assessment date.

Overall survival will be defined from the first dose of blinatumomab treatment until death due to any cause. Subjects still alive at the time of the analysis will be censored at date last known to be alive.

PFS, duration of MRD-negative status and OS will be summarised with KM analyses.

10.4.4 Safety Endpoints

10.4.4.1 Adverse Events

The Medical Dictionary for Regulatory Activities will be used to code all adverse events to a system organ class and a preferred term. Adverse events of interest (EOI)

categories will be based on search strategies defined by Medical Coding. All adverse event tables will be summarized by treatment group. Treatment-emergent adverse events are events with an onset after the administration of the first dose of blinatumomab treatment.

The subject incidence of adverse events will be summarized for all treatment-emergent adverse events, serious adverse events, adverse events leading to withdrawal of protocol-specified therapy, and fatal adverse events.

Subject incidence of all treatment-emergent adverse events, serious adverse events, adverse events leading to withdrawal of blinatumomab, and fatal adverse events will be tabulated by system organ class and preferred term in descending order of frequency; similar summaries will be repeated for EOs. Time to onset and duration of selected EOs (infection and neurologic events) may also be summarized.

Any serious adverse event that occurs from enrolment through the day before the first dose of blinatumomab (during the run-in period) will be documented and summarised. This applies to all subjects who have been enrolled onto the study, regardless of whether they achieve the MRD-positive status required to start treatment with blinatumomab.

A summary of blinatumomab treatment-emergent adverse events will be tabulated by system organ class, preferred term, and worst grade.

